***Routine Daily PA Pressure Data***

Times recorded by patient PAP measurements added by study staff	
Time of PAP Measurement	_____ : _____ AM/PM (record time)
Morning Medications Taken?	_____ Yes  If yes, when? _____ : _____ AM/PM (record time)  _____ No
Heart Rate	_____ beats/minute
Measurement (study staff)	PA systolic _____ (mmHg)  PA diastolic _____ (mmHg)  PA mean _____ (mmHg)

**Data Collection Form for ALL Clinic Visits After Randomization**

Hospitalization or Emergency Room Visits	
Any hospitalizations or ER visits since your last study visit?	 Yes  No  If yes, for what?   Heart Failure  Syncope  Heart Rhythm  Other cardiac  Kidney/Renal issue  Pulmonary/Lung issue  Other, non-cardiac reason
Medication Data	
Beta Blocker Total Daily Dose	_____ (metoprolol equivalents, mg/d)   Not on a beta blocker  Any dose change since most recent clinic visit?  Yes  No  If there has been a recent dose change, describe:   Increased Dose  Decrease Dose  Dose change: From _____ mg/d to _____ mg/d.
ACEi Total Daily Dose	_____ (captopril equivalents, mg/d)   Not on an ACEi  Any dose change since most recent clinic visit?  Yes  No  If there has been a recent dose change, describe:

	
_____ Increased Dose      _____ Decrease Dose
 
Dose change: From _____ mg/d to _____ mg/d.
 
Any dose change since most recent clinic visit?  _____ Yes      _____ No
 
If there has been a recent dose change, describe:
 
_____ Increased Dose      _____ Decrease Dose
 
Dose change: From _____ mg/d to _____ mg/d.

ARB Total Daily Dose	
_____ (valsartan equivalents, mg/d)
 
_____ Not on an ARB
 
Any dose change since most recent clinic visit?  _____ Yes      _____ No
 
If there has been a recent dose change, describe:
 
_____ Increased Dose      _____ Decrease Dose
 
Dose change: From _____ mg/d to _____ mg/d.

Nitrates	
_____ (total daily dose equivalents, mg/d)
 
_____ Not on nitrates
 
Any dose change since most recent clinic visit?  _____ Yes      _____ No
 
If there has been a recent dose change, describe:
 
_____ Increased Dose      _____ Decrease Dose
 
Dose change: From _____ mg/d to _____ mg/d.

Hydralazine	
_____ (total daily dose equivalents, mg/d)
 
_____ Not on hydralazine
 
Any dose change since most recent clinic visit?          _____ Yes          _____ No
 
If there has been a recent dose change, describe:          _____ Increased Dose          _____ Decrease Dose
 
Dose change: From _____ mg/d to _____ mg/d.

Diuretic Total Daily Dose	
_____ (furosemide equivalents, mg/d)
 
_____ Not on diuretics
 
Any dose change since most recent clinic visit?          _____ Yes          _____ No
 
If there has been a recent dose change, describe:          _____ Increased Dose          _____ Decrease Dose
 
Dose change: From _____ mg/d to _____ mg/d.

Use of thiazide diuretic in past 14 days	
_____ Yes
 
If yes, how many days ago? _____ days
 
_____ No
 
Any dose change since most recent clinic visit?          _____ Yes          _____ No
 
If there has been a recent dose change, describe:          _____ Increased Dose          _____ Decrease Dose

	Dose change: From _____ mg/d to _____ mg/d.
Study Drug # tablets/day	_____ Tablets/day
Was your Study Drug dose changed since your last clinic visit?	_____ Yes      _____ No  If there has been a recent dose change, describe:  _____ Increased Dose      _____ Decrease Dose  Dose change: From _____ mg/d to _____ mg/d.
Side Effect Assessment (within the last 14 days, does the patient report any of the following symptoms that are new or different/worsened)	
Swelling/respiratory distress/angioedema/anaphylaxis	_____ Yes      _____ No  If yes, quantify severity ( check most severe symptom )  _____ Swelling (least severe)  _____ Respiratory Distress  _____ Angioedema  _____ Anaphylaxis (most severe)
Palpitations	_____ Yes      _____ No
Difficulty Breathing/Shortness of Breath	_____ Yes      _____ No
Orthopnea	_____ Yes      _____ No
Paroxysmal Nocturnal Dyspnea	_____ Yes      _____ No
Peripheral Edema	_____ Yes      _____ No
Clinical Assessment	

Orthopnea or paroxysmal nocturnal dyspnea within last 14 days	 Yes If yes, how many days? _____ days  No
Bendopnea within last 14 days	 Yes If yes, how many days? _____ days  No
Dizziness or lightheadedness on standing	 Yes  No dizziness or lightheadedness standing If yes, how often?  Rare  1-2x/week  Only if Stand Quickly  Often
Symptoms limiting bathing and dressing	 Yes If yes, how many days? _____ days  No
Examination	
Heart Rate (sitting)	_____ (bpm)
Rhythm (from EKG)	 NSR  Irregular  Paced
Systolic Blood Pressure (sitting)	_____ (mmHg)
Diastolic Blood Pressure (sitting)	_____ (mmHg)

Systolic Blood Pressure (standing)	_____ (mmHg)
Diastolic Blood Pressure (standing)	_____ (mmHg)
Jugular Venous Pressure	_____ (cmH2O)
S3 present	___ Yes      ___ No
Systolic Murmur	___ Yes      ___ No If yes, how severe? ___ 1/6, ___ 2/6, ___ 3/6, ___ 4/6, ___ 5/6, ___ 6/6
Rales	___ Yes      ___ No If yes, how severe? ___ bases, ___ 1/4, ___ 1/3, ___ >1/2 or more of the way up
Hepatomegaly	___ Yes      ___ No If yes, how severe? ___ 1-3cm below costal margin, ___ 4-6cm below costal margin, ___ >6cm below costal margin
Peripheral Edema	___ None    ___ Trace    ___ 1+    ___ 2+
Laboratory Data	
Urine Pregnancy Test (for women of childbearing age)	_____ (Not Pregnant) _____ (Pregnant) * If pregnant, must discontinue Entresto or ACEi/ARB immediately
CardioMEMS Measurements (recorded by staff in clinic)	
PA Systolic Pressure (at rest)	_____ (mmHg)
PA Diastolic Pressure (at rest)	_____ (mmHg)
PA Mean Pressure (at rest)	_____ (mmHg)

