## V. STUDY PROCEDURES

### a. Visit Schedule and Assessments

Over the course of the study, patients will come in for a total of 10 clinic visits (baseline visit, 6 during the intensive phase and 3 during the longitudinal phase) during which the following parameters will be measured:

Visit	Enroll/ Baseline Assmnt.	Intensive Phase						Longitudinal Phase		
		Week 2 Visit	Week 4 Visit	Week 6 Clinic Visit	Week 8 Visit	Week 10 Visit	Week 12 Clinic Visit	Week 18 Clinic Visit	Week 24 Clinic Visit	Week 32 Clinic Visit
Inclusion/ Exclusion	X									
Informed Consent	X									
Physical Exam	X	X	X	X	X	X	X	X	X	X
Symptom and Side Effect Assessment		X	X	X	X	X	X	X	X	X
PAP Recording CardioMEMS	X	X	X	X	X	X	X	X	X	X
6 Minute Walk Test	X			X			X			X
NT-ProBNP & BNP/NT- ProBNP	X			X			X			X
*Safety Labs		X (Group A)			X (Group B)					
Urine Pregnancy Test for Women of Childbearing Age	X									
Quality of Life (KCCQ)	X			X			X			X
Double Master's step test	X			X			X			X
Handrip test	X			X			X			X
Stroop color test	X			X			X			X

*\*Safety labs (potassium and creatinine) will also be drawn within 2 weeks any dose change of either Entresto or ACEi/ARB*

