***ALL CLINIC VISITS AFTER RANDOMIZATION:***

- **Hospitalization or ED visit since last visit? No / Yes, if yes, When**
- **If so, cause:**
  - HF/Syncope or Heart rhythm/ Other cardiac / Renal / Pulmonary
  - Other non-cardiac
- **Medication Data**
  - Beta blocker total daily dose (metoprolol equivalents, mg/d), any change since the last visit?
  - ACEi no/yes (if yes, total daily dose in captopril equivalents, mg/d) , any change since the last visit?
  - ARB no/yes (if yes, total daily dose in valsartan equivalents, mg/d), any change since the last visit?
  - Nitrate no/yes (if yes, total daily dose mg), any change since the last visit?
  - Hydralazine no/yes (if yes, total daily dose mg), any change since the last visit?
  - Diuretic total daily dose (furosemide equivalents, mg/d) , any change since the last visit?
  - Use of thiazide diuretic in past 14 days (no/yes) if yes, # days, any change since the last visit?
  - Study drug # tablets / day
- **Side Effect Assessment**
  - Swelling/respiratory distress/angioedema/anaphylaxis (yes/no)
  - Decreased urinary output (yes/no)
  - Palpitations (yes/no)
  - New/changed difficulty breathing (yes/no)
  - New/changed orthopnea, paroxysmal nocturnal dyspnea, peripheral edema (yes/no)
- **Clinical Assessment**
  - History:
    - Orthopnea within last 14 days (no/yes) If yes, # days
    - Bendopnea within last 14 days (no/yes) If yes, # days
    - Dizziness or lightheadedness on standing (no/yes)
      - If yes, rare / 1-2 x weekly / only if stand quickly / often
    - Symptoms limiting bathing and dressing (no/yes) If yes, #days
  - Examination
    - HR sitting
    - Rhythm (from EKG) regular (SR/paced/
    - SBP/ DBP mmHg sitting /// SBP/DBP mmHg standing
    - Jugular venous pressure (estimated cmH20)
    - S3 yes/ no
    - Systolic murmur (0,1,2,3,4)

- Rales (absent/bases/one-quarter/one third up)
- Hepatomegaly no/yes if yes, 1-3, 4-6, > 6 cm)
- Peripheral edema (none/trace/1+/2+/3+/4+)
- Laboratory Data
  - Urine pregnancy test for women of childbearing age
- PA systolic/ diastolic/ mean pressures at rest (in clinic, mmHg)

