#### **d. Adverse Event Reporting Guidelines**

All of the following events will be collected for review by the independent reviewer and reported to Novartis Pharmaceuticals (along with the relevant randomization codes): All serious adverse events (SAE), all reports of drug exposure during pregnancy, all non-serious adverse events, all reports of misuse and abuse of the study drug, other medication errors, and uses outside what is foreseen in the protocol (irrespective of whether a clinical event has occurred). Any member of the study team can report a potential adverse event. Since Entresto is an FDA approved drug and it will be using it for its FDA approved indication, any adverse events thought to be related to Entresto will be reported FDA's MedWatch program, in keeping with standard practice. Given the mechanism of action of the drug, angioedema is an event of special interest, and all angioedema-like events will be submitted for independent review. Any adverse events that are deemed "significant" by the independent reviewer will also be reported to the Partners IRB.

An SAE is defined as any adverse event (appearance of or worsening of any pre-existing) undesirable sign(s), symptom(s) or medical conditions(s) which meets any one of the following criteria:

- is fatal or life-threatening
- results in persistent or significant disability/incapacity
- constitutes a congenital anomaly/birth defect
- requires inpatient hospitalization or prolongation of existing hospitalization, unless hospitalization is for:

- routine treatment or monitoring of the studied indication, not associated with any deterioration in condition (specify what this includes)
- elective or pre-planned treatment for a pre-existing condition that is unrelated to the indication under study and has not worsened since signing the informed consent
- treatment on an emergency outpatient basis for an event not fulfilling any of the definitions of a SAE given above and not resulting in hospital admission
- social reasons and respite care in the absence of any deterioration in the patient's general condition
- is medically significant, i.e. defined as an event that jeopardizes the patient or may require medical or surgical intervention.

All malignant neoplasms will be assessed as serious under “medically significant” if other seriousness criteria are not met.

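### The side-effect checklist looks back only 14 days, but longitudinal visits are 6 to 8 weeks apart, so its items go unasked for 14 of the 20 open-label weeks

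*Combined protocol and SAP*

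**What the plan says.** Section VI.f contains the "Data Collection Form for ALL Clinic Visits After Randomization". Its Side Effect Assessment block opens with the limit "within the last 14 days, does the patient report any of the following symptoms that are new or different/worsened". That header governs "Swelling/respiratory distress/angioedema/anaphylaxis", and also palpitations, shortness of breath, orthopnea, paroxysmal nocturnal dyspnea and peripheral edema.

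Section V.a plans ten visits: a baseline visit, then "6 during the intensive phase and 3 during the longitudinal phase". A symptom and side-effect assessment is marked at every visit after baseline: weeks 2, 4, 6, 8, 10 and 12, then the "Week 18 Clinic Visit" and visits at weeks 24 and 32.

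Three other places bear on the same items:

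- Section V.e, in its list for all visits after randomization, names the side-effect items without any recall period. It includes one item that the form lacks: "Decreased urinary output (yes/no").
- The hospitalization item on the same form covers the whole interval: "Any hospitalizations or ER visits since your last study visit".
- Section IX.d states that "angioedema is an event of special interest, and all angioedema-like events will be submitted for independent review", and calls for serious and non-serious adverse events to be collected, with no time limit.

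**The concern.** A 14-day look-back is complete only when visits are at most 14 days apart. That holds through week 12 and stops holding afterwards, yet the form does not change. Take a patient whose lip swells at week 14, resolves in two days and leads to no emergency visit. At week 18 the correct answer to the question as printed is no. Staff who follow the form exactly will record no event.

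This sits badly with Section IX.d, which wants every angioedema-like event reviewed, and with Section IX.c, where the side-effect information obtained in clinic is among the data that the independent reviewer sees. The placing of the gap also matters. Section V.b allows the dose to be raised at each clinic visit, so the weeks after a change made at a longitudinal visit come at the start of the interval, while the 14-day window reaches only its end. For those weeks the one side-effect enquiry specified is a nurse call at 2 to 3 days.

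Nothing in the documents suggests that the limit was chosen for the longer intervals. Section V.e has none, and the hospital/ER item beside it runs from the previous visit.

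**Working it through.** **Inputs**

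- Look-back window: 14 days, or 2 weeks (form in Section VI.f).
- Visit weeks: 2, 4, 6, 8, 10, 12, 18, 24, 32, with randomization taken as week 0 (Section V.a).
- Open-label Entresto: weeks 13 to 32 in both groups (Section IV.b).
- Stated length of the later phase: 20 weeks (Section I.c).
- Entresto supply: 32 weeks in Group A, 26 weeks in Group B (Section VIII.a).

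**The plan's own figure.** 32 − 12 = 20 weeks, which agrees with the stated length. The documents give no coverage percentage to reproduce.

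**Formula.** For each interval between visits, weeks covered = min(2, interval length), and weeks unasked = interval length − weeks covered.

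| Interval (weeks) | Length | Covered | Unasked |
|---|---|---|---|
| 0 to 12 (six intervals of 2) | 12 | 12 | 0 |
| 12 to 18 | 6 | 2 | 4 |
| 18 to 24 | 6 | 2 | 4 |
| 24 to 32 | 8 | 2 | 6 |
| **12 to 32** | **20** | **6** | **14** |

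- Longitudinal phase: 14/20 = 70% unasked.
- Intensive phase: 0/12 = 0% unasked.
- Whole study: 14/32 = 43.8% unasked.
- Share of Entresto time: Group A 14/32 = 43.8%; Group B 14/26 = 53.8%.

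**After the change.** If the look-back runs from the previous visit, each interval is covered in full: 6 + 6 + 8 = 20 of 20 weeks, with 0% unasked.

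**Which events the gap can hide.** An event is missed by every scheduled enquiry only if all of the following hold:

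1. It falls under one of the checklist items.
2. It is over, and has not recurred, by the 14 days before the next visit.
3. It led to no hospital or ER visit. If it did, the full-interval item records the visit, though that item has no angioedema category and the cause would go under a broader heading.
4. It was not found at a call after a dose change.
5. The patient did not mention it to any member of the team.

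**The case against.** The strongest reply is that the checklist is not the trial's adverse event system. Section IX.d requires all serious and non-serious events to be collected without a time limit, lets any team member report one, and sends angioedema-like events to review however they come to light. Section IX.c has potential events reviewed as they occur. The side effects that Section VII.b calls major (hypotension, hyperkalemia, renal dysfunction) are followed elsewhere: sitting and standing blood pressure at every visit, a dizziness item with no recall limit, and potassium, urea nitrogen and creatinine at weeks 24 and 32 and after any adjustment of study medication. Patients are also called every few days about their pressure trends (Section V.c).

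All of this stands, and it rules out several stronger readings.

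- A reader might infer that 70% of the open-label period has no adverse event capture. The documents do not support that; the 70% applies only to the items under the 14-day header. What remains is that Section IX.d describes no scheduled question, and the trend calls concern pressures and medication, so an event that nobody asks about and nobody volunteers can still be lost.
- A reader might infer that the form is the sole feed to the independent review and the harm guideline. Section IX.c names clinic side-effect information as one input among several and does not tie the guideline to this form.
- A reader might infer a biased treatment comparison. The randomized period, weeks 0 to 6, is fully covered. After week 12 both groups take the same drug on the same schedule, and no listed endpoint uses the checklist.

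The expected number of missed angioedema events is also tiny. Taking the 0.2% that the protocol cites from a trial with a median follow-up of 27 months, 20 × 0.002 = 0.04 events, and 0.04 × 0.70 = 0.028 would fall in unasked time, even before allowing for the much shorter exposure here. This is only illustrative, and it does not speak to milder swelling, palpitations or breathing symptoms.

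Finally, a fixed 14-day window keeps yes/no rates comparable from visit to visit. That is a genuine merit. It serves a description of current symptoms, though, and not a search for events since the last contact.

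**Conclusion.** The point holds as a gap in scheduled questioning: 14 of 20 open-label weeks (70%) are unasked for the items under the 14-day header, against none of weeks 0 to 12. The figure assumes visits on their nominal weeks and no unscheduled visits; the documents give no visit windows. It measures time without a question, not events missed.

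The practical loss is confined to transient, non-hospitalized events that patients do not volunteer. It leaves the efficacy results and the randomized comparison untouched, and cumulative counts from this checklist should not be compared between the two phases. The consequence is modest, but the form, Section V.e and Section IX.d do not agree on what should be elicited, and the correction is nearly free.

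A reader might also infer that the form's single tick for the most severe symptom loses angioedema events. It does not: a tick for angioedema is enough to bring the event within the review duty of Section IX.d, so that layout is a matter of preference and no part of this point.

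**What to change.** In Section VI.f, change the header of the Side Effect Assessment so that the look-back runs from the last study visit, matching the hospital/ER item on the same form. State the same period beside the item list in Section V.e. Leave the 14-day items in the Clinical Assessment block (orthopnea, bendopnea) as they are, so that current symptoms stay comparable across visits.

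As a minor item, reconcile the urinary-output question: Section V.e lists it and the form omits it, so either add the row or remove it from the list. Renal function is measured by laboratory tests in any case.

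The change needs no extra visit or test. It has two costs. Recall over 6 to 8 weeks is poorer than over 2. The window will also vary from 2 to 8 weeks, so yes/no rates per visit will tend to rise with the interval and should be reported against interval length.

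### The post-randomization visit form keeps only the worst of swelling, respiratory distress, angioedema and anaphylaxis, with no site of swelling, so an unlabelled angioedema-like event cannot be recognised from it

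*Combined protocol and SAP*

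**What the plan says.** The data collection form for clinic visits after randomization (Section VI.f) has a Side Effect Assessment block. Its first row is a single yes/no item, "Swelling/respiratory distress/angioedema/anaphylaxis". If the answer is yes, staff are told to "check most severe symptom" from a list running from swelling, marked as least severe, through respiratory distress and angioedema to anaphylaxis, marked as most severe. The variable list in Section V.e plans the same four-term item as one yes/no. Neither place asks for the site or onset date of the swelling.

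The same block has separate yes/no rows for "Difficulty Breathing/Shortness of Breath", orthopnea, paroxysmal nocturnal dyspnea, peripheral edema and palpitations.

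Section IX.d says that "angioedema is an event of special interest, and all angioedema-like events will be submitted for independent review". It does not define angioedema-like, and it does not say which answers on the visit form lead to that review. Section IX.c gives the independent reviewer, blinded to group and working from de-identified data, the side-effect information from clinic visits among the material to go through.

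**The concern.** Section IX.d uses a category wider than diagnosed angioedema: it wants anything resembling it sent for review. To serve that, the form has to preserve what was seen, not only the label someone chose. A one-tick rule on a ranked list discards every lower-ranked finding. Swelling is ranked lowest, so it is discarded whenever anything else is ticked.

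The combination that matters is swelling together with respiratory distress in a patient whom nobody at the visit has called angioedema. It is stored as respiratory distress. What is at stake is narrow: whether a blinded reviewer working from the clinic side-effect data can notice such a case and ask for more. No efficacy result depends on it.

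**Working it through.** The plan states no figure for this point, so there is none to reproduce. The check is an enumeration, a comparison of fields, and a calculation of scale.

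**1. What the one-tick rule stores**

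Inputs: the four terms and their list order, from the Section VI.f form. Only the two ends carry a severity label, so the ranking of respiratory distress below angioedema is read from list order.

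Non-empty combinations of four findings: 2^4 − 1 = 15. Each is stored as its highest-ranked member.

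| Stored value | Combinations mapped to it |
|---|---|
| Swelling | 1 |
| Respiratory distress | 2 |
| Angioedema | 4 |
| Anaphylaxis | 8 |
| Total | 15 |

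- Swelling is present in 2^3 = 8 combinations and kept in 1.
- Respiratory distress is the stored value for two combinations: respiratory distress alone, and swelling with respiratory distress. They cannot be told apart.
- Angioedema is present in 8 combinations: 4 stored as angioedema, 4 as anaphylaxis, 0 as swelling or respiratory distress.
- Of the 6 possible pairs, 3 are stored as anaphylaxis, 2 as angioedema and 1 as respiratory distress. So 5 of 6 keep angioedema or anaphylaxis, and the only ambiguous pair is swelling with respiratory distress.

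**2. Whether another field recovers the lost swelling**

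Take three patients, none labelled as angioedema, each with breathing trouble reported:

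| Field on the form | Respiratory distress only | Plus swelling of the legs | Plus swelling elsewhere |
|---|---|---|---|
| Combined item | Yes | Yes | Yes |
| Box ticked | Respiratory distress | Respiratory distress | Respiratory distress |
| Breathing difficulty row | Yes | Yes | Yes |
| Peripheral edema row | No | Yes | No |

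The peripheral edema row separates the second patient from the first. Nothing in these rows separates the third from the first. The examination fields (heart rate, rhythm, blood pressure, jugular venous pressure, third heart sound, murmur, rales, liver, peripheral edema) do not record swelling at other sites either.

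**3. Scale**

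Inputs: an angioedema rate of 0.2% on Entresto and 0.1% on ACE inhibitor (Section V.b, Toxicities, and Section VII.b), and 20 patients (Power Analysis). Both groups receive Entresto by the end, so all 20 count.

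- Expected cases at 0.2%: 20 × 0.002 = 0.04.
- Chance of at least one: 1 − (1 − 0.002)^20 = 1 − 0.998^20 ≈ 0.039, or about 3.9%.
- At the lower cited rate of 0.1%: 20 × 0.001 = 0.02 expected, and 1 − 0.999^20 ≈ 0.020.

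These figures are for angioedema. The documents give no rate for angioedema-like events that go unlabelled.

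**The case against.** The strongest reply is that the tick box is not the safety system. Section IX.d collects all serious and non-serious adverse events and lets any team member report one. Sections IX.b and IX.c send potential adverse events to the independent reviewer promptly, and have that reviewer look at all clinical and safety data each time five more patients are enrolled. Section V.b has a nurse telephone within days of a dose change to ask about side effects, and gives round-the-clock access to staff during washout. A yes with respiratory distress ticked is itself a visible positive. All of this stands, and it keeps the point small. It does not remove it: an event reaches the adverse-event route only if someone recognises it as one, and the reviewer cannot recover a finding that was never stored.

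Four stronger readings are tempting, and the documents do not support them.

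- A reader might infer that the event of special interest is lost among heart failure symptoms. It is not. Angioedema has its own box, and in none of the 8 combinations containing it is it stored as swelling or respiratory distress.
- A reader might infer that this form is the only scheduled prompt. The nurse calls, the physical examination at each visit and the question about hospital and emergency visits are others.
- A reader might infer that nearly every yes would be congestion. No document gives a rate for that. The sheet limits answers to new or changed symptoms and gives breathlessness, orthopnea and edema their own rows.
- A reader might infer that the item's count matters for comparing the drugs. The Statistical Analysis section plans no analysis of it, and with 0.04 expected cases no form layout would make a comparison of angioedema informative.

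It can also be said that treating swelling with respiratory distress as angioedema-like is a clinical judgement the documents do not make. That is fair. The form does group these terms with angioedema in one item, but the definition belongs to the investigators.

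**Conclusion.** The point holds in a limited form and is of minor severity. The recording rule discards information bearing on the protocol's own event of special interest in one identifiable situation: non-peripheral swelling with respiratory distress that nobody has labelled angioedema. From the clinic side-effect data that case is indistinguishable from respiratory distress alone. Recognised angioedema is captured unless anaphylaxis is ticked, and that tick also stands out.

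The conclusion assumes that the middle ranks follow list order, that staff follow the one-tick instruction, and that the investigators would regard at least some such combinations as angioedema-like. The figure of 0.04 expected cases further assumes that the cited 0.2% carries over to these 20 patients. The pulmonary pressure endpoints and their analyses are unaffected.

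**What to change.** In the Section VI.f form and the matching Section V.e list, replace the ranked item with four separate yes/no rows, one per term. Add the site and onset date whenever swelling is answered yes. Have the investigators state on the form which answers, alone or together, count as angioedema-like and go to the independent review in Section IX.d. That definition is theirs to write.

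The cost is a form revision and a slightly longer visit sheet. No visit, test, endpoint or analysis changes.
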